7.6.2 Measurability of tumor lesions at baseline

7.6.2.1 Definitions

- **Measurable disease:** The presence of at least one measurable lesion. If the measurable disease is restricted to a solitary lesion, its neoplastic nature will be confirmed by cytology/histology prior to treatment.
- **Measurable lesions:** Tumor lesions that can be accurately measured in at least one dimension (longest diameter to be recorded) as ≥ 10 mm with CT.
 - Bone lesions are considered measurable only if assessed by CT and have an identifiable soft tissue component that meets these requirements (soft tissue component ≥ 10 mm with CT).
 - Malignant lymph nodes must be ≥ 15 mm in the short axis to be considered measurable; only the short axis will be measured and followed.

All tumor measurements must be recorded in millimeters (or decimal fractions of centimeters). Tumor lesions situated in a previously irradiated area, or in an area subjected to other loco-regional therapy, are usually not considered measurable unless there has been demonstrated progression in the lesion.

- **Non-measurable lesions:** All other lesions (or sites of disease), including small lesions, are considered non-measurable disease. Bone lesions without a measurable soft tissue component, leptomeningeal disease, ascites, pleural/pericardial effusions, lymphangitis cutis/pulmonis, lymphangitic involvement of lung or skin and abdominal masses followed by clinical examination, are all non-measurable. Nodes that have a short axis < 10 mm at baseline are considered non-pathological and should not be recorded or followed.

- **Target lesions:** When more than one measurable tumor lesion or malignant lymph node is present at baseline, all lesions up to a maximum of 5 (or 3, if only three are present) lesions in total (and a maximum of 2 lesions per organ) representative of all involved organs should be identified as target lesions, and will be recorded and measured at baseline. Target lesions should be selected on the basis of their size (lesions with the longest diameter), be representative of all involved organs, but in addition should be those that lend themselves to reproducible repeat measurements. Note that pathological lymph nodes must meet the criterion of a short axis of ≥ 15 mm by CT and only the short axis of these nodes will contribute to the baseline sum. At baseline, the sum of the target lesions (longest diameter of tumor lesions plus short axis of lymph nodes; overall maximum of 5) is to be calculated and recorded.
- **Non-target lesions:** All non-measurable lesions (or sites of disease), including pathological nodes (those with short axis ≥ 10 mm but < 15 mm), plus any measurable lesions over and above those listed as target lesions are considered non-target lesions. Measurements are not required, but these lesions should be noted at baseline and should be followed as present or absent.

All baseline evaluations should be performed as closely as possible to the beginning of treatment and every 8 weeks during treatment and planned treatment breaks.

7.6.2.2 Methods of measurements

CT of the thoracic/abdominal/pelvic cavities (preferably with IV contrast) is the best currently available and reproducible method to measure lesions selected for response assessment in metastatic CRC. This protocol has defined measurability of lesions on CT scan based on the assumption that CT slice thickness is 5 mm or less. When CT scans have slice thickness greater than 5 mm, the minimum size for a measurable lesion should be twice the slice thickness.

- Evaluation will be done every 8 weeks.
- The same method of assessment and the same technique should be used to characterize each identified and reported lesion at baseline and during follow-up.
- While on study, all target lesions recorded at baseline should have their actual measurements recorded on the CRF at each subsequent evaluation.
- If it is the opinion of Study Radiologist that the lesion has likely disappeared, the measurement should be recorded as 0 mm. If the lesion is believed to be present and is faintly seen but too small to measure, a default value of 5 mm should be assigned.

For lesions which fragment/split add together, the longest diameter of the fragmented portions will be measured. For lesions which coalesce, the maximal longest diameter for the 'merged lesion' will be measured.

7.6.3 RECIST version 1.1

All patients will have their best response from the start of study treatment until the end of treatment, classified as such:

- **Complete response (CR):** Disappearance of all target and non-target lesions. Pathological lymph nodes must have short axis measures < 10 mm (note: continue to record the measurement even if < 10 mm and considered CR). Tumor markers must have normalized. Residual lesions (other than nodes < 10 mm) thought to be non-malignant should be further investigated (by cytology or positron emission tomography) before CR can be accepted.
- **Partial response (PR):** At least a 30% decrease in the sum of measures (longest diameter for tumor lesions and short axis measure for nodes) of target lesions, taking as reference the baseline sum of diameters. Non-target lesions must be non-PD.
- **Stable disease (SD):** Neither sufficient shrinkage to qualify for PR nor sufficient increase to qualify for PD, taking as reference the smallest sum of diameters on study.
- **Progressive disease (PD):** At least 20% increase in the sum of diameters of measured lesions taking as references the smallest sum of diameters recorded on study (including baseline) and an absolute increase of ≥ 5 mm. Appearance of new lesions will also constitute PD (including lesions in previously unassessed areas). In exceptional circumstances, unequivocal progression of non-target disease may be accepted as evidence of disease progression, where the overall tumor burden has increased sufficiently to merit discontinuation of treatment, for example where the tumor burden appears to have increased by at least 73% in volume (which is the increase in volume when all dimensions of a single lesion increase by 20%). Modest increases in the size of one or more non-

target lesions are *not* considered unequivocal progression. If the evidence of PD is equivocal (target or non-target lesions), treatment may continue until the next assessment, but on further documentation, the earlier date must be used.

CR or PR may be claimed only if the criteria for each are met at a subsequent time point at least 8 weeks later.

Assignments of timepoint response using RECIST v1.1:

Response: First time point	Subsequent time point	BEST overall response	Also requires
CR	CR	CR	Normalization of tumour markers, tumour nodes < 10 mm
CR	PR	SD, PD or PR (see comment*)	
CR	SD	SD provided minimum criteria for SD duration met, otherwise, PD	
CR	PD	SD provided minimum criteria for SD duration met, otherwise, PD	
CR	NE	SD provided minimum criteria for SD duration met, otherwise NE	
PR	CR	PR	
PR	PR	PR	
PR	SD	SD	
PR	PD	SD provided minimum criteria for SD duration met, otherwise, PD	
PR	NE	SD provided minimum criteria for SD duration met, otherwise NE	
NE	NE	NE	

* may consider PR providing initial "CR" likely PR on subsequent review – then original CR should be corrected. Recurrence of lesion after true CR is PD.

7.6.4 iRECIST

In the experimental arm, iRECIST will be used in the case of new lesion(s) or increase in size of known lesion(s), and if the patient is clinically deteriorating. This is categorized as *immune-unconfirmed progressive disease* (iUPD). An *immune-confirmed progressive disease* (iCPD) is only assigned if at next assessment after iUPD (4–8 weeks later) additional new lesions appear or an increase in size of new lesions is seen (≥ 5 mm for sum of new target lesion or any increase in new non-target lesion). The appearance of new lesions when none have previously been recorded can also confirm iCPD.

However, if progression is not confirmed but instead tumor shrinkage occurs (compared with baseline), which meets the criteria of *immune-complete response* (iCR), *immune-partial response* (iPR), or *immune-stable disease* (iSD), then the bar is reset so that iUPD needs to occur again (compared with nadir values) and then be confirmed (by further growth) at the next assessment, for iCPD to be assigned. If no change in tumor size or extent from iUPD occurs, then the time point response would again be iUPD. This approach allows atypical responses, such as delayed responses that occur after pseudoprogression, to be identified, further understood, and better characterized.

Response criteria are essentially based on a set of measurable lesions identified at baseline as target lesions, and, together with other lesions that are denoted as non-target lesions, followed until disease progression.

For direct comparison of iRECIST with RECIST v1.1 [Seymour *et al.*, 2017], please refer to **Appendix 2**.

iCR or iPR may be claimed only if the criteria for each are met at a subsequent time point at least 8 weeks later.

Assignments of timepoint response using iRECIST:

	Timepoint response with no previous iUPD in any category	Timepoint response with previous iUPD in any category
Target lesions: iCR; non-target lesions: iCR; new lesions: no	iCR	iCR
Target lesions: iCR; non-target lesions: non-iCR/non-iUPD; new lesions: no	iPR	iPR
Target lesions: iPR; non-target lesions: non-iCR/non-iUPD; new lesions: no	iPR	iPR
Target lesions: iSD; non-target lesions: non-iCR/non-iUPD; new lesions: no	iSD	iSD
Target lesions: iUPD with no change, or with a decrease from last timepoint; non-target lesions: iUPD with no change, or decrease from last timepoint; new lesions: yes	Not applicable	New lesions confirm iCPD if new lesions were previously identified and they have increased in size (≥ 5 mm in sum of measures for new lesion target or any increase for new lesion non-target) or number; if no change is seen in new lesions (size or number) from last timepoint, assignment remains iUPD
Target lesions: iSD, iPR, iCR; non-target lesions: iUPD; new lesions: no	iUPD	Remains iUPD unless iCPD is confirmed on the basis of a further increase in the size of non-target disease (does not need to meet RECIST 1.1 criteria for unequivocal progression)
Target lesions: iUPD; non-target lesions: non-iCR/non-iUPD, or iCR; new lesions: no	iUPD	Remains iUPD unless iCPD is confirmed on the basis of a further increase in sum of measures ≥ 5 mm; otherwise, assignment remains iUPD
Target lesions: iUPD; non-target lesions: iUPD; new lesions: no	iUPD	Remains iUPD unless iCPD is confirmed based on a further increase in previously identified target lesion iUPD in sum of measures ≥ 5 mm or non-target lesion iUPD (previous assessment need not have shown unequivocal progression)
Target lesions: iUPD; non-target lesions: iUPD; new lesions: yes	iUPD	Remains iUPD unless iCPD is confirmed on the basis of a further increase in previously identified target lesion iUPD sum of measures ≥ 5 mm, previously identified non-target lesion iUPD (does not need to be unequivocal), or an increase in the size or number of new lesions previously identified

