5.5 Duration of therapy

The **control arm** will consist of intermittent treatment with the Nordic FLOX regimen in terms of 8 cycles (16 weeks) before a break until disease progression, when therapy is reintroduced and administered for another 8 cycles before a new break. This go-and-stop schedule, which is chosen because continuous FLOX treatment commonly causes unacceptable toxicity in the palliative setting, will be continued until progressive disease on ongoing therapy (defining PFS in terms of failure of treatment strategy), unacceptable toxicity, withdrawal of consent, or death, whichever occurs first.

The estimated median PFS in the control arm is 9 months (*i.e.*, 39 weeks), as detailed in [Chapter 10](#). During this period, it is assumed that the ‘average’ patient will receive 1 full go-and-stop treatment sequence, consisting of 16 weeks of active therapy followed by 8 weeks of break until disease progression, before the second treatment period results in progressive disease after 16 weeks on ongoing therapy; hence, a PFS of 40 weeks. During the entire treatment, this patient will receive 2 sequences of active therapy, each containing 8 FLOX cycles.

The **experimental arm** will consist of repeat 2 cycles of the Nordic FLOX regimen followed by 2 cycles of nivolumab for a total of 8 individual cycles (16 weeks) before a break until disease progression, when therapy is reintroduced and administered for another total of 8 individual cycles before a new break. This go-and-stop schedule will be continued until progressive disease on ongoing therapy (defining PFS in terms of failure of treatment strategy), unacceptable toxicity, withdrawal of consent, or death, whichever occurs first.

[figure not shown]

Figure 4 – the experimental treatment arm.

The estimated median PFS in the experimental arm is 18 months (*i.e.*, 78 weeks), as detailed in [Chapter 10](#). During this period, it is assumed that the ‘average’ patient will receive 3 full go-and-stop treatment sequences, each consisting of 16 weeks of active therapy followed by 8 weeks of break until disease progression, before the fourth treatment period results in progressive disease after 8 weeks on ongoing therapy; hence, a PFS of 80 weeks. During the entire treatment, this patient will receive 4 sequences of active therapy, each containing 4 cycles each of FLOX and nivolumab.

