7.6.8 Response duration

This will be measured from the time of randomization, or until the first date that recurrent or progressive disease is objectively documented. Patients who have not had PD/iCPD at the time of final analysis will be censored at the date last known to be alive and progression-free.

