ORR is defined as the percentage of patients with a confirmed CR or PR. The proportion of participants achieving at least PR will be summarized with corresponding 95% CI for each treatment arm. The difference between the trial arms in the proportion of participants achieving at least PR will also be presented with corresponding 95% CI. The difference between participants achieving at least PR and remaining participants will be assessed using logistic regression adjusting for treatment group and stratification factors. Odds ratios with corresponding 95% CI and *p*-values will be presented for all variables incorporated in the model.

SSCRR is defined as the percentage of patients with a confirmed resection of metastatic disease with microscopically free margin (R0). Corresponding analyses as those to be performed for ORR will be applied for SSCRR.

DOR is defined as the time from the first documentation of CR/iCR or PR/iPR to disease progression. DOR Kaplan-Meier curves will be drawn and compared by log-rank test. The median DOR with corresponding 95% CI will be presented by treatment group. Stratified analyses will be performed as well. The Cox proportional hazards model, adjusting for the stratification factors, will also be used to compare DOR between the treatment groups. HR, 95%CI and *p*-values will be presented for all variables incorporated in the model.

OS is defined as the time from randomization to death of any cause. The same analyses as for DOR will be performed for OS.

The assumptions for the statistical method considered will be assessed by using standard techniques. In the case the assumptions are not met, the necessary adjustments for methods specified above will be introduced and reported.

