Appendix 2 – RECIST for immune-modulating therapies (iRECIST)

Comparison of RECIST v1.1 and iRECIST:

	RECIST 1.1	iRECIST
Definitions of measurable and non-measurable disease; numbers and site of target disease	Measurable lesions are ≥ 10 mm in diameter (≥ 15 mm for nodal lesions); maximum of five lesions (two per organ); all other disease is considered non-target (must be ≥ 10 mm in short axis for nodal disease)	No change from RECIST 1.1; however, new lesions are assessed as per RECIST 1.1 but are recorded separately on the case report form (but not included in the sum of lesions for target lesions identified at baseline)
Complete response, partial response, or stable disease	Cannot have met criteria for progression before complete response, partial response, or stable disease	Can have had iUPD (one or more instances), but not iCPD, before iCR, iPR, or iSD
Confirmation of complete response or partial response	Only required for non-randomised trials	As per RECIST 1.1
Confirmation of stable disease	Not required	As per RECIST 1.1
New lesions	Result in progression; recorded but not measured	Results in iUPD but iCPD is only assigned on the basis of this category if at next assessment additional new lesions appear or an increase in size of new lesions is seen (≥ 5 mm for sum of new lesion target or any increase in new lesion non-target); the appearance of new lesions when none have previously been recorded, can also confirm iCPD
Independent blinded review and central collection of scans	Recommended in some circumstances—eg, in some trials with progression-based endpoints planned for marketing approval	Collection of scans (but not independent review) recommended for all trials
Confirmation of progression	Not required (unless equivocal)	Required
Consideration of clinical status	Not included in assessment	Clinical stability is considered when deciding whether treatment is continued after iUPD

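### The ORR response window runs to the end of treatment, which is not reconciled with restarting therapy after a break progression or with the RECIST 1.1 rule in Appendix 2

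*Protocol*

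**What the plan says.** - **Response window.** Protocol 7.6.3: "All patients will have their best response from the start of study treatment until the end of treatment". CR and PR must be confirmed at least 8 weeks later, and PR is judged against the baseline sum of diameters.
- **ORR.** Protocol 10.4.5: "ORR is defined as the percentage of patients with a confirmed CR or PR". SAP 5.1 and 5.2 say the same. None of these gives a time window.
- **Go-and-stop schedule.** Protocol 5.5, control arm: 8 cycles "before a break until disease progression, when therapy is reintroduced and administered for another 8 cycles before a new break". The experimental arm follows the same pattern. The strategy ends at progression on ongoing therapy, unacceptable toxicity, withdrawal of consent or death.
- **Expected sequences.** Average control patient: "During the entire treatment, this patient will receive 2 sequences of active therapy, each containing 8 FLOX cycles". Average experimental patient: "During the entire treatment, this patient will receive 4 sequences of active therapy, each containing 4 cycles each of FLOX and nivolumab".
- **RECIST 1.1 rule on order.** Protocol Appendix 2, on CR, PR and SD: "Cannot have met criteria for progression before complete response, partial response, or stable disease". In the iRECIST column, iUPD may precede a response but iCPD may not.
- **iRECIST.** Protocol 7.6.4 applies it in the experimental arm. Section 7.6.7 pools iCR with CR and iPR with PR as reporting categories.
- **Duration.** Protocol 10.4.5 starts DOR at the first documented response. Section 7.6.8 measures response duration from randomisation, "until the first date that recurrent or progressive disease is objectively documented".

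**The concern.** In most trials the end of treatment and the first progression nearly coincide, so a window to the end of treatment does little harm. Here they are separated by design. A patient with SD in the first sequence, progression in the break and PR in the second sequence is a responder under 7.6.3. Under Appendix 2 the same patient is a non-responder.

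Two things are at stake. First, if later sequences count, the arm that stays longer on strategy has more chances to record a first response, and ORR stops being separate evidence of activity. Second, if the choice of rule is left until the data are in hand, the set of responders for both ORR and DOR depends on a decision the plan has not made.

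**Working it through.** **Sequence counts reproduce.** Control: 16 + 8 + 16 = 40 weeks, 2 sequences, against a median of 9 months (39 weeks). Experimental: 3 × 24 + 8 = 80 weeks, 4 sequences, against 18 months (78 weeks). The documents give no response rate or power for ORR.

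**Reading A: literal 7.6.3 window.**

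Assumptions, not in the documents:
- r = first-sequence ORR, 40% in both arms.
- q = chance that a patient with no earlier response has a first confirmed response in a restarted sequence, equal in both arms and constant over sequences.
- The number of restarted sequences k is independent of response.

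Fixed counts (k = 1 v 3): ORR = 1 − (1 − r)(1 − q)^k.

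Exponential PFS with 24-week sequences: k = floor(T/24), so P(k ≥ j) = 2^(−24j/39) in the control arm and 2^(−24j/78) in the experimental arm. Then ORR = r + (1 − r) × q × Σ (1 − q)^(j−1) P(k ≥ j). The cap of 130 weeks is the 30-month experimental-arm follow-up (30 × 52/12) and allows j = 1 to 5.
- Control P(k ≥ j): 0.653, 0.426, 0.278, 0.182, 0.118. The sum is 1.66, so the mean is 2.66 sequences.
- Experimental P(k ≥ j): 0.808, 0.653, 0.527, 0.426, 0.344. The sum is 2.76, so the mean is 3.76 sequences.

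Example at q = 5%: the weighted sums are 1.561 and 2.550. Control ORR = 0.40 + 0.60 × 0.05 × 1.561 = 44.7%. Experimental ORR = 0.40 + 0.60 × 0.05 × 2.550 = 47.6%.

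| q | Fixed 2 v 4: ORR %, gap | Exponential, capped: ORR %, gap | Exponential, uncapped: gap |
|---|---|---|---|
| 0 | 40.0 v 40.0, 0 | 40.0 v 40.0, 0 | 0 |
| 2% | 41.2 v 43.5, 2.3 | 41.9 v 43.2, 1.3 | 2.5 |
| 5% | 43.0 v 48.6, 5.6 | 44.7 v 47.6, 3.0 | 5.3 |
| 10% | 46.0 v 56.3, 10.3 | 48.8 v 54.2, 5.3 | 8.3 |
| 15% | 49.0 v 63.2, 14.2 | 52.5 v 59.7, 7.2 | 10.0 |

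Gaps are in percentage points, from unrounded values. They scale with (1 − r): for r = 30%, multiply by 0.7/0.6; for r = 50%, by 0.5/0.6. If PFS is equal, P(k ≥ j) is the same in both arms and the gap is zero at any q.

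**Reading B: Appendix 2 applied.** A control patient with PD in a break cannot become a responder later. In the experimental arm the same growth may be classed as iUPD. Therapy restarts, and shrinkage that meets the iPR criteria against baseline resets the assessment (7.6.4). Section 7.6.7 then puts that iPR in the same category as PR. One route to response is open in one arm only. Its size cannot be computed from the documents. Whether iCR and iPR enter ORR at all is also unsettled: 10.4.5 names CR or PR for ORR, but includes iCR and iPR for DOR.

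**DOR.** For illustration, take a first response at week 8 and first progression at week 24. Section 10.4.5 gives 24 − 8 = 16 weeks. Section 7.6.8 gives 24 weeks.

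**The case against.** **Appendix 2 already settles it.** The sentence stands under the RECIST 1.1 heading, 7.6.1 makes RECIST 1.1 the primary method, 7.6.4 has lesions followed until progression, and Appendix 2 states the rule on order. This has force: a reader might infer that the plan orders post-progression responses to be counted, and the documents do not say that. But Appendix 2 cannot be assumed to override the body. The same table says that confirmation of response is needed only in non-randomised trials, while 7.6.3 requires it in this randomised one. Neither 7.6.3 nor 10.4.5 refers to the rule. Even if it governs, Reading B leaves the arms unequal.

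**The gap is speculative.** This largely stands. No document gives q. A patient who has never responded and has just progressed must fall 30% below the original baseline and have that confirmed, which points to low values. A reader might take the 6 to 14 points from fixed counts at q = 5 to 15% as the expected distortion; that ignores the spread of PFS times. For scale, the 95% confidence half-width for an ORR difference with 50 per arm near 40% is 1.96 × √(2 × 0.4 × 0.6/50) = 19 points.

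**Extra sequences are a treatment effect, so this is not bias.** That is partly right. Best response over the whole strategy could be a legitimate companion measure. It would have to be named as such, and it would not be independent of PFS.

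**Negative response durations.** A reader might infer these: progression at week 24 and PR at week 32 would give −8 weeks. That takes the start from 10.4.5 and the end from 7.6.8. Neither definition alone produces it, since 7.6.8 starts at randomisation. What the text supports is two conflicting start points.

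**Conclusion.** The point holds as an unreconciled definition, not as proof that ORR will be biased. Two stated rules classify the same patient differently, and the ORR definition does not choose between them.

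- Under the literal window, ORR would partly repeat PFS. With r = 40%, the planned medians and exponential PFS capped at 130 weeks, the gap is about 3 to 7 points for q of 5 to 15%. It is about 1 (capped) to 2.5 (uncapped) points at q = 2%, and zero if q = 0 or PFS is equal. Both r and q are assumptions.
- Under Appendix 2, that gap closes for RECIST 1.1 responses, but an asymmetry of unknown size remains, because only the experimental arm can record a response after iUPD.
- DOR has two conflicting start points.

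ORR and DOR are secondary end points. Primary PFS and the sample size are not affected. The wording should still be settled before database lock, so that the set of responders is not chosen with the data in view.

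**What to change.** In protocol 7.6.3 and 10.4.5 and SAP 5.1/5.2:

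1. Define ORR as best confirmed RECIST 1.1 response from randomisation to the first RECIST 1.1 PD, identically in both arms.
2. Use the same responders for DOR, measured from first response to the next progression, and align 7.6.8 with this.
3. Report iRECIST responses, and responses in restarted sequences, separately as supportive data. For the latter, use the patients who started that sequence as the denominator.

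**Cost.** Wording only. Scans are already scheduled every 8 weeks through treatment and breaks, no treatment rule changes, and 10.4.1 allows changes to the analysis plan until database lock. The reported ORR may be lower. Against the literal window, at r = 40% and q of 5 to 15% with the cap, the fall would be about 5 to 12 points in the control arm (44.7 to 52.5%, down to 40%). In the experimental arm it would be about 8 to 20 points (47.6 to 59.7%, down to 40%). Against the Appendix 2 reading, the loss is limited to iCR and iPR after iUPD, which would no longer count in the main ORR but would still be shown.

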5.7.2.4 Continuing nivolumab with suspected progression

Accumulating evidence indicates that a minority of subjects treated with immune-modulating therapy may derive clinical benefit despite initial evidence of disease progression, such as inflammatory reaction simulating progression, so-called pseudo-progression. Subjects may, at the discretion of Clinical Investigator, continue study treatment in the setting of suspected progression until progression is confirmed, in accordance with the evaluation algorithm detailed for RECIST/iRECIST (*c.f.*, [Paragraph 7.6](#)). If Clinical Investigator believes that the subject continues to derive clinical benefit by continuing treatment, the subject should continue monitoring/assessments according the same schedule as patients without tumor progression, with more frequent radiologic assessment if clinically indicated (see below).

Subjects may continue study treatment beyond initial (suspected) progression only if they meet the following criteria:

- Subject is in stable performance status (ECOG 0–1) and tolerates study treatment.
- Treatment will not delay intervention to prevent imminent complications.
- There is overall clinical benefit as judged by Clinical Investigator.

Radiographic assessment should be repeated after suspected progression as clinically required in order to determine whether there has been a decrease in the tumor size or continued progression. Potential for clinical benefit should be balanced by clinical judgment as to whether the subject is clinically deteriorating and unlikely to receive benefit from continued study treatment. Study treatment will be permanently discontinued upon confirmation of progression.

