7.6 Tumor imaging and assessment of disease procedures

7.6.1 Evaluation of efficacy

The imaging assessments will be performed by CT, typically a thoracic/abdominal/pelvic CT scan. Tumor treatment response will be assessed according to RECIST v1.1 as the primary method and iRECIST as the secondary method. After baseline tumor assessments, evaluation of tumor response will be performed every 8 weeks (± 7 days). Additional MR scans or other radiologic evaluations will be performed if indicated.

All radiologic examinations will be transmitted to Study Radiologist at Akershus University Hospital within 1 working day after the scan is performed. A radiologist at the actual study center will evaluate the images for incidental findings that may have a therapeutic consequence (e.g., pulmonary embolism, immune therapy-related findings that require emergency actions).

Study Radiologist will be blinded to patient treatment, but will be informed about treatment breaks in the go-and-stop schedule. Study Radiologist will primarily assess tumor measures according to RECIST v1.1. If disease progression is concluded by means of RECIST v1.1, Study Radiologist will also assess tumor measures according to iRECIST. The radiology report will detail the criteria used for Clinical Investigator to make a decision about further study treatment (*c.f.*, [Paragraph 5.7.2.4](#)).

PFS will be calculated from the day of randomization to first recorded disease progression according to RECIST v1.1 or iRECIST when applicable, or death. Patients who have not had disease progression at the time of final analysis will be censored at the date last known to be alive and progression-free.

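### The opening paragraph of Protocol 7.6.4 confirms iRECIST progression only through new lesions, while its own table also confirms it through growth of known lesions, so experimental-arm PFS can depend on which is followed

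*Protocol*

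**What the plan says.** Protocol 7.6.4 uses iRECIST in the experimental arm "in the case of new lesion(s) or increase in size of known lesion(s), and if the patient is clinically deteriorating", and calls that state iUPD. The same paragraph says that the iCPD label "is only assigned if at next assessment after iUPD (4–8 weeks later) additional new lesions appear or an increase in size of new lesions" occurs; the size rule it then gives in brackets concerns new lesions only. One further route follows: "The appearance of new lesions when none have previously been recorded can also confirm iCPD".

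The timepoint table in 7.6.4 is wider. Where target lesions are at iUPD and there are no new lesions, its entry is "Remains iUPD unless iCPD is confirmed on the basis of a further increase in sum of measures" of at least 5 mm. Two further rows without new lesions allow confirmation by non-target growth.

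Four other places bear on this:

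- Protocol 7.6.1: "If disease progression is concluded by means of RECIST v1.1, Study Radiologist will also assess tumor measures according to iRECIST". No clinical condition is attached.
- Protocol Appendix 2: the new-lesion row has nearly the same confirmation sentence, but restricts it to the new-lesion category. Another row says "Clinical stability is considered when deciding whether treatment is continued after iUPD".
- Protocol 7.6.6: progression is dated by RECIST v1.1 PD in the control arm and by iCPD in the experimental arm.
- SAP 5.1 and 5.2: PFS rests on RECIST v1.1 or, when applicable, iRECIST. No confirmation rule is given.

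**The concern.** A blinded central reader needs one rule for turning iUPD into iCPD. Section 7.6.4 supplies two, and nothing says which prevails. They differ for the patient whose known lesions keep growing while no new lesion appears.

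At stake is the primary endpoint. If iCPD is not assigned, 7.6.6 gives no progression date for an experimental-arm patient, and PFS runs on to a later confirmation, death or censoring. Control-arm patients are dated by RECIST v1.1 PD and are untouched, so an error of this kind lengthens PFS in one arm only. The same classification feeds the response category (7.6.7), response duration (7.6.8) and the radiology report on which further study treatment is decided (7.6.1).

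The trigger wording adds a second uncertainty, about which patients enter iRECIST assessment at all.

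**Working it through.** The plan states no figure on this point, so there is none to reproduce. The check sets the passages side by side and then follows one case.

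**Confirmation after iUPD**

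| Finding at the next scan | 7.6.4 opening paragraph | 7.6.4 table |
|---|---|---|
| More new lesions, or growth of new lesions | iCPD | iCPD |
| Target sum up by at least 5 mm, no new lesions | stays iUPD | iCPD |
| Further non-target growth, no new lesions | stays iUPD | iCPD |

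The last two lines cannot both hold. Appendix 2 suggests how the conflict arose: its limit applies to confirmation through new lesions, and the 7.6.4 paragraph repeats the sentence without that qualifier. A limit on one category thus reads as a limit on all.

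**One case (illustrative measurements)**

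Inputs: target sum 60 mm at nadir, 75 mm at the scan where iUPD is assigned, 90 mm at the next scan, no new lesions.

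1. First increase: 75 − 60 = 15 mm, and 15/60 = 25%. Protocol 7.6.3 requires at least 20% and at least 5 mm, so RECIST v1.1 PD is met.
2. Further increase: 90 − 75 = 15 mm, above the table's 5 mm.
3. Table: iCPD, and a progression date under 7.6.6.
4. Opening paragraph: no new lesion, so iUPD remains and 7.6.6 supplies no date.

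Each further scan left at iUPD moves that patient's date by one assessment interval: 4–8 weeks by 7.6.4, or normally 8 weeks, with the option of 4, by 7.6.5. This comes on top of any delay from requiring confirmation at all, which is a separate matter.

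**Trigger**

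- *Joint reading* (lesion finding and deterioration both required): a clinically stable patient with RECIST v1.1 PD is outside iRECIST under 7.6.4 but inside it under 7.6.1. Clinical status would decide whether iUPD is assigned, whereas Appendix 2 uses it only for continuing treatment after iUPD.
- *Additive reading* (deterioration is one more occasion for iRECIST): stable patients remain covered, and that conflict with 7.6.1 disappears. Section 7.6.5 lists suspected clinical progression and iUPD as alternatives, which fits this reading.

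The text does not settle which is meant. The two problems need not push PFS the same way. The confirmation conflict can withhold events in the experimental arm. The joint trigger could instead leave a stable patient classified as RECIST PD at the first scan, which is earlier.

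**The case against.** The strongest reply is that 7.6.4 should be read as a whole. The table is headed as the assignment rule for timepoint responses and is what a radiologist would score from. The second paragraph of the section speaks of confirmation through continued growth when iUPD recurs after a reset. It also says that an unchanged tumor stays iUPD, which implies that change in size matters. This stands as far as it goes. A reader might infer that growth of known lesions never confirms, or that progression is misclassified in every experimental-arm patient who progresses without new lesions. The documents support neither. They support only that it *can* be misclassified, by a reader who follows the opening paragraph. The reply does not remove the conflict, because no passage ranks the table above the prose.

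Other tempting inferences also go too far:

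- *iRECIST is reserved for deteriorating patients.* This needs the joint reading, which the wording permits but does not force.
- *Growth has no minimum size.* Under 7.6.1, iRECIST follows RECIST v1.1 PD, so the 20% and 5 mm rule has already been met.
- *5.7.2.4 contradicts 7.6.4 on scan classification.* Section 5.7.2.4 asks that "Subject is in stable performance status (ECOG 0–1) and tolerates study treatment", but as a condition for continuing treatment. A patient may be iUPD and off treatment, and 7.6.5 keeps imaging patients who stop without progression.
- *The blinded reader cannot apply the trigger.* No passage gives that reader clinical status, but this is silence, and 7.6.1 offers a rule that needs none.

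Finally, PFS is defined in 7.6.1, 10.4.1 and SAP 5.2 by RECIST v1.1 or, when applicable, iRECIST. The absence of a PFS event in the case above therefore rests on 7.6.6, and on iUPD having been assigned.

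**Conclusion.** The confirmation rule is wrong as written: the opening paragraph of 7.6.4 contradicts the table in its own section and drops a qualifier that Appendix 2 retains. Given the iCPD dating in 7.6.6, following the prose can delay or omit PFS events in the experimental arm alone, in that arm's favour. Following the table avoids this.

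The size is unknown. The documents do not say how many progressions occur by growth of known lesions without new lesions, nor which text readers would use. A simulated hazard ratio would reflect only the assumed share and the assumed time from progression to death, so none is offered as evidence.

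The trigger wording is ambiguous and needs clarifying; it conflicts with 7.6.1 and Appendix 2 only if read as a joint condition. No net direction is claimed for the two issues together.

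**What to change.** Amend the opening paragraph of 7.6.4:

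- Let iRECIST assessment and iUPD follow RECIST v1.1 PD, as in 7.6.1, and take clinical status out of the measurement rule.
- Assign iCPD by any route in the 7.6.4 table: target sum, non-target growth, or number or size of new lesions. Restore Appendix 2's restriction of the new-lesion sentence to that category.

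Give the central reader the same rule as a written instruction before unblinding.

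Confirmed progression ends study treatment under 5.7.2.4, so the wording on treatment continuation in 7.6.4, 5.7.2.4 and Appendix 2 must also be reconciled. No clinical rule is proposed here.

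The cost is one paragraph of protocol text and a reader instruction. No new data are needed.
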